### **6.3 Measures to Minimize Bias: Randomization and Blinding**

A web-based central randomization system will be developed by the SIREN DCC and installed on the WebDCU™ study website. Allocation will be fixed using a 1:1 allocation ratio. The objective of randomization is to prevent possible selection bias by providing random treatment assignment to each subject and to prevent accidental treatment imbalances for known prognostic variables. Variables that will be included in the randomization scheme are: age (treated as a continuous variable) and site. Site is included in the randomization scheme to avoid severe treatment imbalances within each site. Randomization will occur via the study-specific password-protected website accessed by an authorized research coordinator or investigator at the clinical site. If, in rare circumstances, the web system is not available, the coordinator or investigator will have access to emergency randomization procedures that will allow the site to randomize the subject. Subjects will be considered randomized in this trial at the time of randomization, regardless of whether or not they receive the assigned study treatment.

The primary outcome assessment in this trial will be performed by study team members who are blinded to study group allotment. To test the effectiveness of blinding procedures, subjects will be asked at the Day 2 and Day 15 follow-up assessment to which treatment arm they believe they were assigned and how confident they are in their response. If the subject becomes knowledgeable of their treatment assignment at any point during study participation, this will be documented in the study database. Regardless of unblinding, the subject will remain in the study and be part of the analysis population.

### **6.4 Concomitant Therapy and Hospitalization**

Concomitant medications will be documented on the CRF. We will not enroll patients already in another clinical trial. Subjects should not enroll in another interventional trial as an outpatient while in this clinical trial.

In the event that a subject worsens and is admitted to a hospital, that subject will have met the primary endpoint of this trial. We will not restrict that subject from enrolling in another trial if eligible, especially because other trials may be the only access for potential COVID-19 therapies. In particular, control subjects should be eligible for compassionate use CP, though this trial cannot guarantee CP will be available at a site precisely when the subject is hospitalized. Patients in either arm who develop severe/critical disease are not precluded from receiving compassionate use CP after meeting the primary endpoint, if this therapy is available for routine clinical care at the institution where they receive care.

## **7. Participant Discontinuation/Withdrawal**

### **7.1 Participant Discontinuation/Withdrawal from the Study**

Participants are free to withdraw from participation in the study at any time upon request. The reason for participant discontinuation from the study will be recorded on the Case Report Form (CRF). Subjects who are randomized and subsequently withdraw informed consent will not be replaced.

### **7.2 Loss to Follow-Up**

To attain a high rate of follow up (>90%), the study team will request multiple phone numbers (home, cell phones, pagers, etc) and addresses from the subject and his/her relatives, friends, primary doctor (if available), clergy and clinics. At the time of consent and enrollment, subjects

will be asked to provide the address and telephone number of the place where the subject will likely reside following discharge.

Following ED discharge, a blinded research coordinator will telephone subjects every other day for a health status inquiry and to maintain and update tracking information. During follow-up phone calls, if medical concerns are raised, subjects will be referred to their usual care provider or to emergency care if urgent. In the event that the research coordinator cannot reach a subject or an informant, the coordinator will continue to call frequently for up to 2 weeks after the last scheduled contact before considering a subject lost to follow-up. Subjects cannot be deemed "Lost to Follow-up" without the C3PO Operations Committee approval. The site PI must present a case to the C3PO Operations Committee that includes the efforts exerted to locate the study subject. The Site PI may be asked to continue their efforts prior to approval.

## 8. Study Assessments and Procedures

### 8.1 Efficacy Assessments

Trained study personnel who are blinded to study group allotment will interview participants via telephone every other day during the first 14 days of the study and on day 15 (window: days 14, 15 and 16) and 30 (window: days 29, 30, 31, 32, 33) to ascertain efficacy and safety endpoints. Assessments will be performed either by study personnel at local sites or by a centralized pool of trained personnel. Data will be documented in WebDCU.

Central caller assessments completed within 1 day of the time point will be counted as qualifying and not considered missing.

On study days 15 (window: days 14, 15, 16) and 30 (window: 29, 30, 31, 32, 33), participants will be asked to return for research blood draws. If there is no follow-up due to lack of patient response, the patient will be considered lost to follow-up.

#### 8.1.1 Primary Endpoint

These events can be ascertained from the subject or informant report during follow-up calls, electronic health record review, death notices, or direct contact with the subject during follow-up visits. Thus, we have multiple opportunities to collect and confirm the primary endpoint, minimizing risk of missing data.

Subjects will meet the primary endpoint of the study (1) if they are admitted to a hospital as an inpatient/observation status for any reason during the 15 days following randomization, (2) if they have an emergency department or urgent clinic visit during the 15 days following randomization, or (3) die outside the hospital during the 15 days following randomization. Scheduled medical follow-up visits or rechecks will not meet the definition of emergency care.

#### 8.1.2 Secondary Endpoints (clinical)

These endpoints can be ascertained from the subject or informant report during follow-up calls, supplemented by review of health records. Surveys and assessments from day 0-14 that are completed within 1 day of the time point will be counted as qualifying and not considered missing (for example day 4 assessment may be done on day 4 or 5).

**COVID-19 illness severity:** We will quantify COVID-19 illness severity using a 8-point ordinal scale developed by a World Health Organization (WHO) committee. We will record the worst illness severity rating observed during the 30 days following randomization:

WHO's COVID Ordinal Scale for Clinical Improvement

- 8 = Death
- 7 = Hospitalized, intubated, mechanically ventilated and requiring additional organ support (pressors, renal replacement therapy)
- 6 = Hospitalized, intubated and mechanically ventilated
- 5 = Hospitalized on non-invasive ventilation or high flow nasal cannula
- 4 = Hospitalized on supplemental oxygen by mask or nasal prongs
- 3 = Hospitalized not on supplemental oxygen
- 2 = Not hospitalized with limitation in activity (continued symptoms)
- 1 = Not hospitalized without limitation in activity (no symptoms)

*COVID-19 illness severity (outpatient):* An adaptation of the WHO scale, based on the quality of symptoms reported by the subject, can quantify outpatient disease severity among patients at home (scores 1-2 on the WHO scale). This 5-point COVID Outpatient Ordinal Outcomes scale was adapted for outpatient use from Harrell 2020

(<http://hbiostat.org/proj/covid19/bayesplan.html>). This scale is hierarchical where 1 is the highest severity (hospitalization) and 5 is the lowest severity.

#### COVID Outpatient Ordinal Outcomes Scale

- 1 = patient requires care in the hospital
- 2 = patient requires care in the ED or urgent care
- 3 = patient at home with symptoms rated as moderate (defined as fever, shortness of breath, abdominal pain)
- 4 = patient at home with symptoms rated as mild (defined as afebrile, constitutional symptoms (flu-like illness) without shortness of breath)
- 5 = patient in their usual state of health

Worsening of symptoms is defined as any subject admitted to the hospital (level 1), seen in the emergency room (level 2), a patient who reports increased symptoms of 2 levels on the scale over a 24 hour period, or a patient who reports increased symptoms of 1 level observed for a 48 hour period.

*Symptom inventory:* On study days 2, 4, 6, 8, 10, 12, 14, 15 and 30, we will record the burden of symptoms listed by the Centers for Disease Control and Prevention (CDC) as typical of COVID-19 illness. For purposes of this trial symptoms include any symptoms of COVID-19 illness listed by the CDC case definition guidance at the time of enrollment. These include but are not limited to the following: .

- Fever or chills
- Cough
- Shortness of breath or difficulty breathing
- Fatigue
- Muscle or body aches
- Headache
- New loss of taste or smell
- Sore throat
- Congestion or runny nose
- Nausea or vomiting
- Diarrhea
- Abdominal pain
- Limitations of activities because of COVID-19 symptoms

Refer to the Manual of Procedures for the latest CDC list of COVID-19 symptoms.

*Hospital-free days:* We will record the number of days a subject was not admitted to a hospital during the first 30 days following randomization.

*All-cause mortality:* We will record death from any cause that occurred during the first 30 days following randomization.

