### **Secondary Endpoints**

- Worst severity rating on the WHO's COVID Ordinal Scale for Clinical Improvement during the 30 days following randomization
  - Death
  - Hospitalized on invasive mechanical ventilation or ECMO
  - Hospitalized on non-invasive ventilation or high flow nasal cannula
  - Hospitalized on supplemental oxygen
  - Hospitalized not on supplemental oxygen
  - Not hospitalized with limitation in activity (continued symptoms)
  - Not hospitalized without limitation in activity (no symptoms)
- Time to disease progression on the COVID Outpatient Ordinal Outcome Scale censored at 15 days after randomization
  - Patient requires care in the hospital
  - Patient requires care in the ED or urgent care
  - Patient at home with symptoms rated as moderate (defined as fever, shortness of breath, abdominal pain)
  - Patient at home with symptoms rated as mild (defined as afebrile, constitutional symptoms (flu-like illness) without shortness of breath)
  - Patient in their usual state of health
- Hospital-free days during the 30 days following randomization
- All-cause mortality at 30 days

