#### **9.2.4 Analysis of Secondary and Exploratory Outcomes**

This study is designed to test the primary hypothesis; however, it also offers the opportunity to evaluate important additional secondary and exploratory outcomes. Continuous secondary endpoints will be summarized by the mean and standard deviation with corresponding 95% confidence intervals. Categorical endpoints will be summarized by the sample proportions with exact or asymptotic confidence intervals. For time to event analyses, we will construct Kaplan Meier curves. Our analyses will consider sex as a biological variable that may affect treatment outcomes for COVID-19.

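### The two-level, 24-hour limb of the time-to-progression endpoint does not fit contacts planned 48 hours apart; the one-level limb is ambiguous and death at home is not listed

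*Combined protocol and SAP*

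**What the plan says.** The synopsis lists as a secondary endpoint "Time to disease progression on the COVID Outpatient Ordinal Outcome Scale censored at 15 days after randomization". The scale has five levels, from 5 (usual health) to 1 (hospital care). Level 2 is emergency or urgent care, and levels 3 and 4 are moderate and mild symptoms at home.

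Section 8.1.2 then defines worsening by four routes. Two rest on care received: hospital admission (level 1) and an emergency room visit (level 2). The third route, called the two-level limb here, is "a patient who reports increased symptoms of 2 levels on the scale over a 24 hour period". The fourth route, called the one-level limb here, is "a patient who reports increased symptoms of 1 level observed for a 48 hour period".

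Under Section 8.1, blinded staff "interview participants via telephone every other day during the first 14 days of the study and on day 15". The schedule of activities also marks a symptom inventory on Day 0. Section 8.1.2 accepts assessments "completed within 1 day of the time point will be counted as qualifying", and its example places the Day 4 assessment on Day 4 or Day 5. Section 8.1 gives Day 15 a window of Days 14 to 16.

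On analysis, Section 9.2.4 says "For time to event analyses, we will construct Kaplan Meier curves". It gives no rule for dating a worsening first seen at a contact.

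**The concern.** A change over 24 hours can be seen directly only if ratings are about a day apart, and the protocol describes no daily contact or diary. Two participants with the same illness course could be classified differently because their calls fell on different days.

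The one-level limb has a separate problem. It can mean a change across one 48-hour gap, or a change that then persists for 48 hours. The text also does not say whether the comparison is with baseline or with the previous contact. Two analysts could derive different event counts and times from the same records.

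Finally, the worsening list omits death, and the scale has no level for it. Section 8.1.1 counts death outside hospital in the primary endpoint. As written, a participant who dies at home with no earlier qualifying event has not progressed on this endpoint.

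**Working it through.** **Inputs.** Symptom assessments before censoring fall on Days 0, 2, 4, 6, 8, 10, 12, 14 and 15 (schedule of activities; Section 8.1.2). One study day is treated as 24 hours, which is approximate because study days change at midnight.

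**Nominal gaps.** Gap = later day minus earlier day.
- 0-2, 2-4, 4-6, 6-8, 8-10, 10-12 and 12-14: 2 days each, so seven gaps of 48 hours.
- 14-15: 1 day, so one gap of 24 hours.

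One of 8 intervals fits the 24-hour limb, covering 1 of 15 follow-up days (1/15 = 6.7%). The synopsis, the exploratory endpoint list and the objectives table omit Day 12 from the symptom inventory. If those lists governed, the gap from Day 10 to Day 14 would be 96 hours.

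**Gaps that the windows allow.** The first column follows the Section 8.1.2 example (on the day or one day late). The second reads the window as one day either side.

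| Gap | 0 to +1 day | -1 to +1 day |
|---|---|---|
| 0-2 | 2 or 3 days | 1 to 3 days |
| Each of 2-4 to 12-14 | 1, 2 or 3 days | 0 to 4 days |
| 14-15 | 0, 1 or 2 days | 0 to 3 days |

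For example, Day 2 done on Day 3 and Day 4 done on Day 4 are one day apart. Day 2 done on Day 2 and Day 4 done on Day 5 are three days apart. So 24-hour gaps can occur earlier in follow-up, but through call timing and not by design. The Day 14-15 pair is not guaranteed to be 24 hours apart either.

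**What the 24-hour limb adds.** Two-level worsenings on the scale are 5 to 3, 4 to 2 and 3 to 1. The last two end at level 2 or 1 and are already events, taking the emergency-room route to cover all of level 2, including urgent care. Only 5 to 3 depends on this limb.

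**A 5-to-3 move on the actual contacts.** Suppose level 5 on Day 4, level 3 on Day 6, and level 5 again on Day 8.
- 24-hour limb, calls on Days 4 and 6: not met.
- 24-hour limb, same illness with the first call a day late on Day 5 and still level 5: met.
- One-level limb read as a change across one gap: met on Day 6.
- One-level limb read as sustained: not met. It would be met if the participant were still at least one level worse on Day 8.

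The 24-hour limb therefore decides the outcome only for a 5-to-3 move that is not sustained to the next contact, and only if the one-level limb requires persistence.

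**A 4-to-3 move.** Everyone enters symptomatic (Section 5.1), so this is the more natural worsening at home. Suppose level 4 on Day 4 and level 3 on Day 6. Read as a change across one gap, this is an event on Day 6. Read as sustained, it is no event unless the worsening persists to Day 8, and the date could then be Day 6 or Day 8.

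**The case against.** The strongest reply is that little is lost. Emergency visits and admissions count whatever the call spacing. The 48-hour limb fits the planned schedule and catches sustained worsening. A 5-to-3 move needs a return to usual health and then a relapse to moderate symptoms. Both arms share one schedule with blinded callers, this is one of several secondary endpoints, and Section 9.2.4 says the study is designed to test the primary hypothesis. All of this stands, and it limits the size of the point.

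Some stronger readings are tempting but not supported:
- **The limb can be met only between Days 14 and 15.** This is true of the nominal schedule alone. The windows allow one-day gaps elsewhere.
- **Only about 7% of such worsening would be caught.** The 6.7% is a share of the calendar and does not estimate events lost.
- **A 5-to-3 change from Day 4 to Day 6 is not an event.** It misses the 24-hour limb on nominal days but may qualify under the one-level limb.
- **The plan excludes recall of the days between calls.** The documents are silent on question wording. Section 8.1.2 speaks of what the patient reports and allows informant report and health records.
- **Event times will be treated as exact, or the treatment comparison is biased.** Section 9.2.4 mentions only Kaplan-Meier curves, and nothing shows that coarse dating differs by arm.

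The reply does not resolve the dependence on call timing, the two readings of the one-level limb, or the omission of death.

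**Conclusion.** The point holds with limited reach. The 24-hour limb matches 1 of 8 nominal intervals, and elsewhere whether it is met depends on call timing. Its effect is confined to 5-to-3 moves not sustained to the next contact and to the dating of at-home events. The ambiguity of the one-level limb probably matters more in practice, because it applies to the 4-to-3 move and changes both the count and the dates. The omission of death outside hospital is a plain inconsistency with the primary endpoint.

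This rests on the protocol text alone. The Manual of Procedures and case report forms were not available and might specify recall questions or dating. The number of participants affected cannot be estimated from the documents. The primary endpoint is unaffected. The definition should still be corrected before unblinding, because the at-home part of the endpoint cannot be derived reproducibly as written.

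**What to change.** Amend Section 8.1.2, with matching text in Section 9.2.4, before unblinding:

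1. Define worsening as any of: at least 2 levels worse than the previous completed contact; at least 1 level worse at two successive contacts, against a named reference contact; an emergency or urgent care visit; admission; or death.
2. Date at-home events to the first contact that shows the worsening. Date visits, admissions and deaths from records.
3. State how a missed contact is handled, and how a one-level worsening first seen at Day 15 is treated, since no later contact precedes censoring.
4. Optionally, add a discrete-time or interval-censored analysis as a sensitivity analysis.

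This uses the same calls and the same data. The cost is an amendment to a secondary endpoint definition mid-trial, which should be recorded as made without knowledge of results by arm. Some dependence on spacing remains: a two-level change across one missed call spans 4 days on the nominal schedule (for example Day 4 to Day 8) instead of 2.

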### 1.4 Schedule of Activities

	Study Day										
	0	2	4	6	8	10	12	14	15	30	
Inclusion/Exclusion											
Informed Consent	X										
Demographics	X										
Medical History	X										
Contact Information	X										
ABO type	X										
Randomization	X										
Pre-intervention research blood draw	X										
Administer CP or Placebo											
Post-intervention research blood draw	X										
X											
Research Blood Draw									X	X	
Residual viral media / saliva sample	X										
Assess for Hospitalization		X	X	X	X	X	X	X	X	X	
Vital Status		X	X	X	X	X	X	X	X	X	
Symptom Inventory	X	X	X	X	X	X	X	X	X	X	

Adverse Event Assessment	X	X	X	X	X	X	X	X	X
Review Electronic Medical Record / Death Index	X								X X X

*Study Day 0 is the same as the day of randomization. Day 0 starts from the time of randomization until 23:59 of that calendar day. Day 1 begins at 00:00 on the following day.*

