**1.5.3 Day 30 End of Study**

- Review electronic medical record for hospitalizations or serious adverse events
- Review death notifications for any subjects lost to follow-up

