Determine the effect of CP on prevention of hospitalization	Hospital-free days during the 30 days following randomization	This is a more graded measurement of hospitalization than the binary primary outcome
Determine the effect of CP on mortality	All-cause mortality at 30 days	Critical safety outcome
Determine the effect of CP on the duration of symptoms	Symptom inventory measured using the CDC list of COVID-19 symptoms on days 2, 4, 6, 8, 10, 14, 15, 30	Patient centered outcome relevant to patient experience of illness
Characterize the immunological response to CP administration	Neutralizing antibody titers at days 0 (pre-intervention and post-intervention), 15, and 30 using different methods	Determine if CP administration increases recipient antibody titers that can inhibit virus

Measure change in spike protein IgG titers in CP recipient from pre- to post-CP	Spike protein IgG antibody titers pre and post CP administration using different methods	Determine distribution of CP antibodies into recipient
---	--	--

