### 3.1 Primary Endpoint

*Operational definition of Hospitalization Care in the primary endpoint:*

- The endpoint is determined based on the order to admit the patient to an inpatient hospital bed (including admission to observation status). Patients may board in emergency departments or other outpatient areas awaiting inpatient beds for some time; therefore, the intent to place the patient in an inpatient bed is considered to be hospitalization. Observation in an emergency department observation unit would not count as hospitalization but only as emergency care. In the event that a patient worsens in the emergency department shortly after administration of the intervention and requires admission during that same visit, we will consider that that patient has met this primary endpoint.

*Operational definition of Emergency Care in the primary endpoint:*

- This endpoint is determined based on any presentation to an emergency department or urgent clinic for care. COVID-19 patients may be redirected to special areas adjacent to or outside of the usual emergency department for evaluation and treatment; therefore, the presentation for emergency or urgent care is considered the endpoint rather than physical entry into a specific area.

*Operational definition of Death in the primary endpoint:*

- Patients who die outside the hospital during the 15 days following randomization will meet this endpoint. Death notice or public records can confirm death.

*Justification of the primary endpoint:*

Hospitalization is a hard metric of meaningful worsening of disease.

- Hospitalization is a readily observable and objective outcome. It does not depend on self assessment, does not depend on return to the enrollment site, and can be verified by self-report, proxy-report, or even limited source documents from any admitting hospital or clinic. As such, it has low vulnerability to missing data or bias.
- The endpoint is a marker for worsening of disease. Hospitalization is a marker for the need of more intensive treatment that cannot be managed as an outpatient and is similar to the criteria used to characterize an adverse event as serious.
- The endpoint matters to patients. The need for hospitalization is a significant and meaningful event for patients. Hospitalization also removes patients from families and support systems further aggravating other symptoms of disease progression.

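### Hospital-free days has no rule for death: counted as written, days after death score as hospital-free, so an early death can score as well as or better than survival with a hospital stay

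*Combined protocol and SAP*

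**What the plan says.** Hospital-free days is a clinical secondary endpoint. Its only operational definition, in section 8.1.2, reads: "We will record the number of days a subject was not admitted to a hospital during the first 30 days following randomization". The synopsis (section 1.2) gives only the name and window: "Hospital-free days during the 30 days following randomization". The table in section 3 links the endpoint to prevention of hospitalization and justifies it in these words: "This is a more graded measurement of hospitalization than the binary primary outcome". Section 3.2 lists it by name.

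For analysis, section 9.2.4 states: "Continuous secondary endpoints will be summarized by the mean and standard deviation with corresponding 95% confidence intervals". Section 9.2.1 applies the intent-to-treat principle, so a patient who dies stays in the analysis and needs a value. The handling rules in section 9.2.3 are written for the primary outcome. In section 4.3, death is not among the criteria for a discontinued subject, and a completed subject must have had the Day 30 visit.

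Death is captured elsewhere. Section 8.1.2 says of mortality: "We will record death from any cause that occurred during the first 30 days following randomization". The same section makes death the worst level of the WHO scale. Section 3.1 covers deaths before any admission: "Patients who die outside the hospital during the 15 days following randomization will meet this endpoint". None of these provisions is linked to the hospital-free count.

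**The concern.** A patient who has died is not admitted to a hospital. The sentence in section 8.1.2 therefore credits every day after death as hospital-free unless the analyst adds a condition that the plan does not contain. Death also ends the chance of admission, so a count meant to show prevention of hospitalization records the worst outcome as successful prevention. The trial's own severity scale puts death last, while this endpoint can rank it level with the best possible course.

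Two things are at stake. First, a mortality imbalance can bias the difference in mean hospital-free days. Second, an analyst who stops the count at death gets a different answer from one who follows the text, and the plan does not say which is intended. That choice should not be left until the data are unblinded.

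**Working it through.** The plan gives no expected mean, SD or power for this endpoint, so there is no stated figure to reproduce. The check has three parts.

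**1. Scores for individual courses.** The 30-day window is from section 8.1.2. The plan does not say which days are counted, so the convention here is an assumption: Days 1 to 30, with the day of admission and the day of in-hospital death counted as hospital days, and the day of a home death not counted as alive and out of hospital. The courses are illustrations, not trial data.

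| Course | Literal count | Alive and out of hospital | Death scored 0 |
|---|---|---|---|
| Home death, Day 2 | 30 | 1 | 0 |
| Admitted Day 5, died Day 10 | 30 - 6 = 24 | 4 | 0 |
| Admitted Day 10, died Day 25 | 30 - 16 = 14 | 9 | 0 |
| Home death, Day 25 | 30 | 24 | 0 |
| Survivor, 10-day stay | 20 | 20 | 20 |
| Survivor, never admitted | 30 | 30 | 30 |

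Under the literal count the Day 2 home death equals the best survivor, and the Day 10 in-hospital death beats the survivor with a 10-day stay. Moving the counting convention by one day does not change that second ordering. Not every death is misplaced against that survivor: the Day 25 in-hospital death scores 14, below 20.

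**2. Effect on the mean difference.** Let m be 30-day mortality in an arm and c the mean number of days credited from death onward among those who die. The literal mean exceeds the alive-and-out mean by m × c. The error in the CP-minus-control difference is therefore m(CP) × c(CP) - m(control) × c(control). If c is the same in both arms, each percentage point of mortality difference moves the result by 0.01 × c:

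- in-hospital death Day 10: c = 20, error 0.20 day
- in-hospital death Day 25: c = 5, error 0.05 day
- home death Day 2: c = 29, error 0.29 day
- home death Day 25: c = 6, error 0.06 day

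With equal c the error favors the arm with more deaths. With unequal c it can reverse. If 2% of controls die in hospital on Day 25 and 1% of CP patients die in hospital on Day 10, the credits are 0.02 × 5 = 0.10 and 0.01 × 20 = 0.20 day, so the pull is toward CP, the arm with fewer deaths.

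**3. Scale.** The revised maximum is 450 per arm (section 1.1). The document gives no SD, so 3 to 6 days is assumed. The 95% half-width is 1.96 × SD × √(2/450):

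- SD 3: 1.96 × 3 × 0.0667 = 0.39 day
- SD 6: 1.96 × 6 × 0.0667 = 0.78 day

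A one-point mortality difference is 4.5 patients per arm. Its error, 0.05 to 0.29 day, is below the half-width throughout. As background, sections 1.2 and 2.2 describe about 5% of cases becoming critical and up to half of that 5% dying, which is at most 0.05 × 0.50 = 2.5% of all cases. No expected mortality is given for the trial population.

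**The case against.** The endpoint is presented as a measure of hospitalization, death has its own endpoint, and the WHO scale already ranks death worst. A mortality imbalance would be visible beside this result. Section 9.2.4 only summarizes continuous secondary endpoints and attaches no decision rule to this one. A sensible analyst might stop the count at death without being told.

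Most of this stands as an argument about size. It does not close the gap, because even a pure hospitalization measure needs a rule for patients who can no longer be admitted, and no section supplies one.

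A reader might infer more than the document supports:

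- **That the plan expressly credits days after death.** It does not. It is silent, and the credit follows from applying the sentence as written.
- **That the bias always favors the arm with more deaths.** This needs similar hospital days before death and similar timing of death in the arms. The reversal shown above rules out the unconditional claim.
- **That the error should be measured against scoring death as 0.** This would give larger figures for late deaths, but that rule is an optional design choice. The plan's stated purpose does not require it, so a departure from it is not an error in the plan.
- **That early home deaths are expected to be common.** Section 3.1 only says that an out-of-hospital death counts toward the primary endpoint. Enrolled patients are judged stable for outpatient management. The Day 2 case shows the extreme.

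**Conclusion.** The point holds as a defect in one definition. Followed literally, section 8.1.2 lets some deaths score level with or above survivors, and the plan contains nothing to prevent it. For deaths between Day 2 and Day 25, the error against an alive-and-out count is about 0.05 to 0.29 day per percentage point of mortality difference, provided timing and place of death are similar in the arms. If they are not, the direction can reverse. A one-point difference stays inside the sampling error under the assumed SD.

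The gap and the misordering are certain from the text. The size is uncertain, because the SD, the trial mortality and the timing of deaths are all assumed. The primary endpoint, the WHO scale and 30-day mortality are not affected, so this is a small but worthwhile correction and does not threaten the trial's main conclusion.

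**What to change.** In section 8.1.2, redefine the endpoint as days alive and not admitted to a hospital through Day 30. State which days count, including Day 0 and the days of admission, discharge and death. Day 0 needs a decision because section 1.4 defines it as a part-day ("Day 0 starts from the time of randomization until 23:59 of that calendar day") and section 3.1 foresees admission during the enrollment visit. Settle both before unblinding.

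The alive condition stops credit after death but does not put every death below every survivor: in the table, a home death on Day 25 still scores 24 against 20. If the sponsor wants deaths at the bottom, scoring any death by Day 30 as 0 is a common option. It makes the endpoint a composite of death and hospitalization, departs from the purpose given in section 3, and ties a death with a survivor hospitalized for all 30 days. If it is used, report 30-day mortality (already planned) and hospital days separately.

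The cost is a sentence or two. No new data source is needed: deaths within 30 days are recorded, hospitalization data are collected (section 1.5), and section 1.5.3 already includes this step: "Review death notifications for any subjects lost to follow-up".
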